3.2 Rationale of study design

This randomized, multi-center, patient and investigator blinded, placebo-controlled study is designed to assess the safety and tolerability of LMB763 relative to placebo in patients with NASH.

Randomization will be initiated at a **2:1** ratio of active to placebo in order to reduce the sample size. The statistical power of the study will be bolstered by using historical control data from trials like the FLINT study to supplement the placebo arm. Multiple sites are necessitated due to the underlying prevalence of NASH defined in publicly available recruitment data. No known differences exist in regional criteria for the histopathological diagnosis of NASH. Since NASH is more common in those self-identified as Asian at lower body mass index (BMI), specific criteria inclusion criteria have been included for this population.

In order to maintain the scientific integrity of the study, the investigator and patient will remain blinded to their treatment allocation and baseline intra-hepatic lipid content. To allow close monitoring of biochemical safety parameters which overlap with efficacy outcomes (eg. ALT) and understanding of performance of exploratory biomarkers, the Novartis Clinical Trial Team (CTT) will be unblinded throughout the study.

To ensure that no bias is introduced by imbalance in severity of disease across different arms of the study, patients will be stratified to active or placebo arms on the basis of BMI.

The duration of 12 weeks of therapy is supported by GLP-toxicology studies of 13 weeks in duration and it is also a suitable timeframe to test the chosen primary endpoints in the study. In the FLINT trial of a less potent FXR agonist, ALT and GGT levels in the blood dropped as early as after 4 weeks of treatment and most of this effect was noted by 12 weeks of therapy ([Neuschwander-Tetri et al 2015](#)).

To keep dietary intake as consistent as possible, patients participating in this study will be instructed to carefully adhere to American Heart Association (AHA) diet or equivalent if there is a country specific recommended diet.

3.3 Rationale for dose/regimen, route of administration and duration of treatment

Corporate Confidential Information

The initial dose of LMB763 was chosen on the basis of safety and likely pharmacological activity. Preliminary analysis suggested that the mean increases in biomarkers of target engagement were higher than anticipated ^{Corporate Confidential Information}. In particular an increase in the FXR responsive marker ALP was noted in context of no increase in GGT or 5'NT. No SAEs have been attributed to LMB763 ^{Corporate Confidential Information}.

Corporate Confidential Information

The duration of the study is based on findings in 2 published studies relating to obeticholic acid ([Mudaliar et al 2013](#); [Neuschwander-Tetri et al 2015](#)), which demonstrate that 12 weeks will provide sufficient timeframe to assess biochemical changes likely to result from improvement to the NASH phenotype. In addition, observations from other studies with surgical ([Jiménez-Agüero et al 2014](#)), diet ([Ryan et al 2013](#)) and pharmacotherapy (CLCQ908A2216) also suggest that 12 weeks is an adequate timeframe to test an effect on liver fat ([Neuschwander-Tetri et al 2015](#)).

Corporate Confidential Information

3.4 Rationale for choice of comparator

Currently there is no licensed pharmacological therapy for patients with NASH. A placebo will be used as a comparator in this study to ensure the effects of LMB763 are related to the study drug. All patients will be encouraged to adhere to local advice regarding diet and exercise regimens.

3.5 Rationale for choice of background therapy

Not applicable

Corporate Confidential Information

3.7 Risks and benefits

As well as the risks and potential risks described in the Investigators' Brochure, there may be unknown risks to LMB763 which may be serious and unforeseen.

The risk to patients in this trial will be minimized by adherence to the eligibility criteria, close clinical monitoring of safety e.g. liver transaminases, dose reduction steps and stopping rules.

Corporate Confidential Information

Women of child bearing potential should be informed that taking the investigational drug may involve unknown risks to the fetus if pregnancy were to occur during the study, and must agree that in order to participate in the study they must adhere to the contraception requirement for the duration of the study. If there is any question that the patient will not reliably comply, they should not be entered in the study.

Pruritus and LDL elevations have been noted in clinical trials with a bile acid derived FXR agonist, but have not been noted in _____ studies with non-bile acid FXR partial or full agonists, LMB763 or LJM452, respectively. Both pruritus and serum lipids will be closely monitored in this study.

A maximum of approximately 442.2 mL of blood is planned to be collected from each patient as part of the study. Additional samples for monitoring of any safety findings may be required, and would be in addition to this volume. Over the course of the 4 to 8 months study period, this is not considered to be a concern for this population.

MRI makes use of powerful magnetic fields and radio waves, which are believed to cause no direct adverse consequences when used within FDA-approved specifications. No MRI-contrast will be administered in this study. Thus in principle, MRI scans can be repeated in the same patient as often as necessary. The MRI scanning equipment may cause a feeling of claustrophobia in susceptible persons; therefore, sensitivity to enclosed spaces should be queried at screening. Refer to eligibility criteria to exclude patients who are not suitable candidates for MRI scanning.

Patients participating in this study might have reductions in hepatic fat; it is possible that this is a clinical benefit. However, 12 weeks treatment is unlikely to be sufficient to provide benefit in reducing hepatic fibrosis. For this reason, liver biopsies are not performed in this study. There may be patient benefit in the ancillary dietary and exercise counseling accompanying the pharmacologic intervention.

3.7.1 Blood sample volumes

A maximum of approximately 442.2 mL of blood is planned to be collected over a period of approximately 22 weeks, from each patient as part of the study. Additional samples required for monitoring of any safety findings would be in addition to this volume. This is not considered to be a risk for this population.

Timings of blood sample collection are outlined in the [Assessment Schedule, Section 8.1](#)

A summary blood log is provided in the Site Operations Manual. Instructions for all sample collection, processing, storage and shipment information will be contained in the Central Laboratory Manual.

See [Section 8.9](#) regarding the potential use of residual samples.

4 Population

The study population will be comprised of male and female adult patients with EITHER histologic evidence of NASH on liver biopsy within 2 years prior to randomization and elevated ALT, OR phenotypic diagnosis of NASH based on elevated ALT, Type 2 diabetes mellitus or elevated HbA1c and increased BMI; full details are outlined in [Section 4.1](#) (Inclusion criteria).

The investigator must ensure that all patients being considered for the study meet the following eligibility criteria. No additional criteria should be applied by the investigator in order that the study population will be representative of all eligible patients.

Patient selection is to be established by checking through all eligibility criteria at screening and baseline. A relevant record (e.g. checklist) of the eligibility criteria must be stored with the source documentation at the study site.

Provided patients meet all other eligibility criteria, patients with a single lab value outside of the allowable range may be considered eligible for enrolment, as long as the abnormal lab value is within 10% of the allowable value. ALT and eGFR values must always fall inside the allowable range as listed in the inclusion and exclusion criteria.

4.1 Inclusion criteria

Patients eligible for inclusion in this study must fulfill **all** of the following criteria:

Cohort 1

1. Informed consent must be obtained before any assessment is performed
2. Male and female patients 18 years or older (at the time of the screening visit)
3. Presence of NASH as demonstrated by ONE of the following:

EITHER

Histologic evidence of NASH based on liver biopsy obtained within 2 years prior to randomization with a diagnosis consistent with NASH, fibrosis level F1, F2 or F3, in the absence of a histological diagnosis of alternative chronic liver diseases

AND

ALT \geq 60 IU/L (males) or \geq 40 IU/L (females)

OR

Phenotypic diagnosis of NASH based on the presence of ALL THREE of the following:

- ALT \geq 60 IU/L (males) or \geq 40 IU/L (females) **AND**
- BMI \geq 27 kg/m² (in patients with a self-identified race other than Asian) or \geq 23 kg/m² (in patients with a self-identified Asian race) **AND**
- Diagnosis of Type 2 diabetes mellitus by having either:
 - HbA1C \geq 6.5%

OR

- Symptoms of diabetes plus hyperglycemia as indicated by
 - fasting plasma glucose ≥ 126 mg/dl (≥ 7.0 mmol/l)
 - two hour plasma glucose concentration ≥ 200 mg/dl (≥ 11.1 mmol/l two hours after 75g anhydrous glucose in an oral glucose tolerance test (OGTT))

OR

- Drug therapy for Type 2 diabetes mellitus (as long as on a stable dose. Refer to [Section 5.2](#))
4. . Patients must weigh at least 40 kg (88 lbs) and no more than 150 kg (330 lbs.) to participate in the study. Inclusion of patients with higher weights up to 200 kg (440 lbs.) may occur if a MRI scanner with a table weight of 200 kg (440 lbs.) is available.
 5. Able to communicate well with the investigator, to understand and comply with the requirements of the study.

Cohort 2

6. Informed consent must be obtained before any assessment is performed
7. Male and female patients 18 years or older (at the time of the screening visit)
8. Presence of NASH as demonstrated by ONE of the following:

EITHER

Histologic evidence of NASH based on liver biopsy obtained within 2 years prior to randomization with a diagnosis consistent with NASH, fibrosis level F1, F2 or F3, in the absence of a histological diagnosis of alternative chronic liver diseases

AND

ALT ≥ 43 IU/L (males) or ≥ 28 IU/L (females) at screening

OR

Phenotypic diagnosis of NASH based on the presence of ALL THREE of the following:

- ALT ≥ 43 IU/L (males) or ≥ 28 IU/L (females) at screening **AND**
- BMI ≥ 27 kg/m² (in patients with a self-identified race other than Asian) or ≥ 23 kg/m² (in patients with a self-identified Asian race) **AND**
- Diagnosis of Type 2 diabetes mellitus by having either:
 - HbA1C $\geq 6.5\%$

OR

- Symptoms of diabetes plus hyperglycemia as indicated by
 - fasting plasma glucose ≥ 126 mg/dl (≥ 7.0 mmol/l)
 - two hour plasma glucose concentration ≥ 200 mg/dl (≥ 11.1 mmol/l two hours after 75g anhydrous glucose in an oral glucose tolerance test (OGTT))

OR

- Drug therapy for Type 2 diabetes mellitus (as long as on a stable dose. Refer to [Section 5.2](#))

9. Liver fat $\geq 10\%$ at baseline as determined by the reading of the central MRI laboratory of locally produced images. The MRI assessment should only be performed after eligibility has been confirmed from all other baseline assessments.
10. Patients must weigh at least 40 kg (88 lbs) and no more than 150 kg (330 lbs.) to participate in the study. Inclusion of patients with higher weights up to 200 kg (440 lbs.) may occur if a MRI scanner with a table weight of 200 kg (440 lbs.) is available.
11. Able to communicate well with the investigator, to understand and comply with the requirements of the study.

4.2 Exclusion criteria

Cohorts 1 and 2

Patients with NASH phenotype fulfilling any of the following criteria are not eligible for inclusion in this study:

1. History of severe hypersensitivity to drugs of any kind or sensitivity to those including pyrazole (eg celecoxib or stanozolol) or an imidazole ring (eg antifungals including ketoconazole, anthelmintics including mebendazole and nitroimidazole antibiotics including metronidazole).
2. Use of other investigational drugs within 5 half-lives of enrollment, or within 30 days whichever is longer; or longer if required by local regulations.
3. Current use of obeticholic acid (OCA).
4. New initiation GLP-1 agonists such as liraglutide, exenatide, lixisenatide, albiglutide or dulaglutide or DPP4 inhibitors such as sitagliptin, vildagliptin, saxagliptin or linagliptin within 3 months of screening.
5. Patients taking medications prohibited by the protocol. See [Section 5.2](#) for further details.
6. Patients on treatment with the following medicines UNLESS they are on a stable dose for at least 1 month before randomization: insulin (no more than 25% change in dose), beta-blockers, thiazide diuretics, fibrates, statins, niacin, ezetimibe, vitamin E (if doses > 200 IU/day; doses > 800 IU/day are prohibited), thyroid hormone, psychotropic medications, estrogen or estrogen containing birth control. For oral anti-diabetic medications, no more than one step-up or step-down in local prescribing guidelines will be allowed.
7. History of treated or untreated malignancy of any organ system, other than localized basal cell carcinoma of the skin or treated cervical intraepithelial neoplasia, within the past 5 years, regardless of whether there is evidence of local recurrence or metastases.
8. Pregnant or nursing (lactating) women, where pregnancy is defined as the state of a female after conception and until the termination of gestation, confirmed by a positive hCG laboratory test.

9. Women of child-bearing potential, defined as all women physiologically capable of becoming pregnant, unless they are using highly effective methods of contraception during dosing and for 5 days (approximately 5 times the terminal half life) after stopping study medication. **Highly effective contraception methods include:**
- Total abstinence (when this is in line with the preferred and usual lifestyle of the patient. Periodic abstinence (e.g., calendar, ovulation, symptothermal, post-ovulation methods) and withdrawal are not acceptable methods of contraception)
 - Female sterilization (have had surgical bilateral oophorectomy with or without hysterectomy) or tubal ligation at least six weeks before taking study treatment. In case of oophorectomy alone, only when the reproductive status of the woman has been confirmed by follow up hormone level assessment
 - Male sterilization (at least 6 months prior to screening). For female patients on the study the vasectomized male partner should be the sole partner for that patient
 - Use of oral (estrogen and progesterone), injected or implanted combined hormonal methods of contraception or placement of an intrauterine device (IUD) or intrauterine system (IUS), or other forms of hormonal contraception that have comparable efficacy (failure rate <1%), for example hormone vaginal ring or transdermal hormone contraception

In case of use of oral contraception women should have been stable on the same pill for a minimum of 3 months before taking study treatment.

Women are considered post-menopausal and not of child bearing potential if they have had 12 months of natural (spontaneous) amenorrhea with an appropriate clinical profile (e.g. age appropriate, history of vasomotor symptoms) or have had surgical bilateral oophorectomy (with or without hysterectomy), total hysterectomy or tubal ligation at least six weeks ago. In the case of oophorectomy alone, only when the reproductive status of the woman has been confirmed by follow up hormone level assessment is she considered not of child bearing potential.

10. Sexually active males will be excluded UNLESS they agree to use a condom during intercourse while taking study medication and for 5 days after stopping study medication and should not father a child in this period. A condom is required to be used also by vasectomized men in order to prevent delivery of the drug via seminal fluid.
11. Current or history of significant alcohol consumption for a period of more than 3 consecutive months within 1 year prior to screening (significant alcohol consumption is defined as more than 20 g/day in females and more than 30 g/day in males, on average) and/or a score on the AUDIT questionnaire ≥ 8 as administered by the site as part of the medical history.
12. Inability to reliably quantify alcohol consumption based upon local study physician judgment.
13. History of drug or alcohol abuse within the 12 months prior to dosing, or evidence of such abuse as indicated by the laboratory assays conducted during screening and baseline. Marijuana use is not allowed if it is determined to be medically inappropriate by the investigator.
14. Prior or planned (during the study period) bariatric surgery (eg, gastroplasty, roux-en-Y gastric bypass).

15. Type I diabetes and uncontrolled diabetes defined as $HbA_{1c} \geq 9.5\%$ within 60 days prior to enrollment.
16. Calculated eGFR less than 60 mL/min (using the MDRD formula)
17. Presence of cirrhosis on liver biopsy or clinical diagnosis.
18. Clinical evidence of hepatic decompensation or severe liver impairment as defined by the presence of any of the following abnormalities:
 - Serum albumin < 32 g/L
 - INR > 1.3
 - Direct bilirubin > 13 mg/L
 - ALT or AST > 5 × ULN
 - Alkaline Phosphatase > 3 × ULN
 - History of grade 2 or greater esophageal varices, ascites or hepatic encephalopathy
 - Splenomegaly
19. Platelet count < $120 \times 10^9/L$.
20. History or presence of other concomitant liver diseases including, but not limited to:
 - Hepatitis B or C virus (HCV, HBV) infection
 - Primary biliary cholangitis (PBC)
 - Primary sclerosing cholangitis (PSC)
 - Alcoholic liver disease
 - Definite autoimmune liver disease or overlap hepatitis
 - Suspected or confirmed Gilbert's syndrome
 - Known bile duct obstruction
 - Suspected or proven liver cancer
21. History of liver transplantation or current placement on a liver transplant list.
22. History of inflammatory bowel disease.
23. Known positivity for Human Immunodeficiency Virus (HIV) infection.
24. History of non-adherence to medical regimens, or patients who are considered by the investigator to be unable to reliably comply with the requirements of the study.
25. Chronic use (i.e. > 3 months immediately prior to baseline visit) of high dose Nonsteroidal Anti-inflammatory Drugs (NSAIDs) as evaluated by investigator.
26. History or current diagnosis of ECG abnormalities indicating significant risk of safety for patients participating in the study such as:
 - Concomitant clinically significant cardiac arrhythmias, e.g., sustained ventricular tachycardia, and clinically significant second or third degree AV block without a pacemaker
 - History of familial long QT syndrome or known family history of Torsades de Pointes
27. Donation or loss of 400 ml or more of blood within eight (8) weeks prior to initial dosing, or longer if required by local regulation.

28. Patients with contraindications to MRI imaging, including:

- Brain aneurysm clip
- Implanted neural stimulator
- Implanted cardiac pacemaker or defibrillator, or presence of intracardiac wires
- Prosthetic heart valves
- Cochlear implant
- Ocular foreign bodies that might be ferromagnetic (e.g., metal shavings)
- Other implanted medical devices (e.g., insulin pumps)
- Metal shrapnel or bullets still in the body
- Severe claustrophobia
- Tattoos (as determined by the Investigator and Imager)
- Weight in excess of MRI machine capacity

29. For those patients that have had a previous biopsy: Significant weight loss (>15%) or change in clinical status (in the opinion of the investigator) since the diagnostic liver biopsy (refer to Inclusion Criterion #3).

No additional exclusions may be applied by the investigator, in order to ensure that the study population will be representative of all eligible patients.

5 Restrictions for Study Patients

Patients must be informed and reminded of the restrictions outlined in this section throughout the study.

5.1 Contraception requirements

Women of child bearing potential must be informed that taking the study treatment may involve unknown risks to the fetus if pregnancy were to occur during the study, and must agree that in order to participate in the study they must adhere to the contraception requirements specified in [Section 4.2](#) (Exclusion criteria). If there is any question that the patient will not reliably comply, they should not be entered or continue in the study.

Sexually active males should be reminded of the requirement to wear a condom for the following reasons:

- To prevent pregnancy in a female partner

AND

- To prevent delivery of investigational drug via seminal fluid to their partner

If there is any question that the patient will not reliably comply, the patient should not be entered or continue in the study. Male patients should be informed that if a female partner becomes pregnant while he is enrolled in the study, contact with the female partner will be attempted to request her consent to collect pregnancy outcome information. Please refer to exclusion criteria ([Section 4.2](#)) for details of contraception requirements for the study.

5.2 Prohibited treatment

Medications or herbal remedies that may have a significant impact on LMB763 metabolism by inhibiting UGT1A1 are prohibited in the study from the first dosing until end of study evaluations have been completed. These include (but not limited to): atazanavir, gemfibrozil, indinavir, itraconazole, ketoconazole, manidipine and zafirlukast and *Silybum marianum* (*milk thistle*) and *Valeriana officinalis* (*valerian*). The non-selective UGT inhibitors diclofenac, probenecid and valproic acid are also prohibited.

Should a patient have an incidental and limited need for a medication to be taken within the restricted pre-dose timeframe (e.g. analgesia following dental surgery, etc.), the sponsor should be advised, as administration of any concomitant medication may require the patient to be replaced. Decisions regarding replacements will be discussed with the sponsor on a case-by-case basis.

There is a potential for LMB763 to increase exposure of drugs metabolized by CYP2C8 (including repaglinide, pioglitazone and rosiglitazone) and those dependent on export by BCRP (potentially glyburide (glibenclamide), atorvastatin, rosuvastatin and pitavastatin). Careful attention should be paid to the drug interaction sections of the prescribing information for these compounds.

Patients on medications specified in [Table 5-2](#) can be included if these medications are deemed by the investigator to be:

- Medically necessary, and
- Dose has been stable for at least 1 month prior to randomization, and
- Dose is believed to remain stable for the duration of the double-blind treatment period.

No new use of these medications is allowed after entering the study, with the exception of drugs to control medically significant elevations in LDL-cholesterol which have been confirmed upon repeat testing.

A 'stable' dose of insulin is defined as being within 25% of the current dose. A stable dose of oral anti-diabetic medications is defined as up to one step-up or step-down in local prescribing guidelines from the dose at randomization. For all other medications listed in [Table 5-2](#), the definition of stable will be left to investigator discretion.

An overview of the prohibited medication is given in [Table 5-1](#), and the summary of permitted medications if on a stable dose is presented in [Table 5-2](#).

Table 5-1 Prohibited medication

Medication	Prohibited
Specific UGT1A1 inhibitors: atazanavir, gemfibrozil, indinavir, itraconazole, ketoconazole, manidipine, and zafirlukast	Any use from first drug intake to end-of-study visit
Herbal remedies inhibiting UGT1A1: Silybum marianum (silymarin, milk thistle) and Valeriana officinalis (valerian)	Any use from first drug intake to end-of-study visit
Non-selective UGT inhibitors: diclofenac, probenecid, valproic acid	Any use from first drug intake to end-of-study visit
Vitamin E	Doses >800 IU/day
GLP-1 agonists such as liraglutide, exenatide, lixisenatide, albiglutide or dulaglutide or DPP4 inhibitors such as sitagliptin, vildagliptin, saxagliptin or linagliptin	Newly initiated use within 3 months prior to screening

Table 5-2 Permitted medications if dose is stable for at least 1 month prior to randomization

Medication
Oral anti-diabetic medications such as metformin, sulfonylureas (including glyburide (glibenclamide), meglitinides (such as repaglinide) and thiazolidinediones (including pioglitazone and rosiglitazone))* Insulin (within 25% of the dose at randomization)** Beta-blockers and thiazide diuretics Fibrates, statins*, niacin, ezetimibe*** Vitamin E**** Thyroid hormone Psychotropic medications (phenothiazines or second generation antipsychotics) Estrogen or estrogen containing birth control

Notes: *There is a potential for LMB763 to increase exposure of drugs metabolized by CYP2C8 (including repaglinide,) and those dependent on export by BCRP (potentially glyburide (glibenclamide), atorvastatin, rosuvastatin and pitavastatin). Careful attention should be paid to the drug interaction sections of the prescribing information for these compounds. For oral anti-diabetic medications, one step up in local prescribing guidelines from the dose at randomization will be allowable; **Unless adjustment is required due to intercurrent illness; ***Unless adjustment is required to treat medically significant increases in LDL that have been confirmed upon repeat testing; ****Only applicable for patients taking >200 IU/day;

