2.2 Secondary objectives

Secondary objectives	Endpoints related to secondary objectives

 To evaluate the pharmacokinetics (PK) of LMB763 in NASH patients. 	
 PK blood collection and analysis (C_{max}, T_{max}, AUC, R_{acc}, etc.).

 To determine the effect of LMB763 on intrahepatic lipid after 12 weeks of treatment. 	
 Percent (%) Liver fat as measured by Magnetic Resonance Imaging (MRI).

 To determine the effect of LMB763 on anthropometric assessments after 12 weeks of treatment. 	
 Weight, BMI, waist-to-hip (WTH) ratio.

 To determine the effect of LMB763 on non-invasive markers of liver fibrosis. 	
 Fibroscan[®] (in a subset of patients) Fibrosis biomarker test (originally known as Fibrotest[®]/FibroSure[®]).

 To determine the effect of LMB763 on fasting lipid profile. 	
 Fasting lipid profile.

 To determine the effect of LMB763 compared with placebo with respect to occurrence and impact of potential itch. 	
 Itch scored on 100 mm visual analog scale (VAS) ratings.

3 Investigational plan

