11.5 Analysis of secondary variable(s)

11.5.1 Efficacy / Pharmacodynamics

Log-transformed ratio to baseline % liver fat and fasting lipid profiles (total cholesterol, HDL, LDL, triglycerides) as well as change from baseline % liver fat, weight, BMI, WTH ratio will be analyzed using the same repeated measures ANCOVA described in [Section 11.4.2](#) with

log-transformed baseline in lieu of baseline as a covariate for lipid parameters. Fibroscan[®] (in a subset of patients), ELF and fibrosis biomarker test data will be analyzed similarly and the log-transformation applied prior to the analysis as needed. For parameters with only one post-treatment measurement an ANCOVA with treatment as a classification factor and baseline (or log-transformed baseline if applicable) as a covariate will be employed. For % liver fat, if historical placebo control data in a similar patient population are identified in the literature or become available from in-house studies later on then they may be incorporated into a Bayesian analysis as described for ALT.

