6.2.3 Statistical model, assumptions and hypotheses

Log-transformed ratio to baseline % liver fat and fasting lipid profiles as well as change from baseline % liver fat, weight, BMI, WTH ratio and itch VAS score will be analyzed. Parameters with more than one post-treatment measurement will be subjected to the same repeated measures ANCOVA described for the primary analysis using log-transformed baseline in lieu of untransformed baseline as a covariate for the log-transformed data analysis. For parameters with only one post-treatment measurement an ANCOVA with treatment as a classification factor and baseline (or log-transformed baseline if applicable) as a covariate will be employed.

Fibroscan® (in a subset of patients), ELF and fibrosis biomarker test data will be analyzed similarly and the log-transformation applied prior to the analysis as needed. For % liver fat, if historical placebo control data in a similar patient population are identified in the literature or become available from in-house studies later on then they may be incorporated into a Bayesian analysis as described for ALT.

The subgroup of subjects with baseline liver fat $\geq 10\%$ may be analyzed separately as needed.

Corporate Confidential Information

7 Statistical methods for safety and tolerability data

All subjects within the Safety analysis set will be included in the safety data analysis.

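### Lipid-lowering drugs may be started or increased for a confirmed LDL rise, but the lipid analysis has no rule for values measured afterwards, so a true LDL increase on LMB763 may be understated at later visits.

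*Protocol*

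**What the plan says.** **The exception.** Protocol 5.2 allows no new use of the Table 5-2 medicines once a patient has entered the study, "with the exception of drugs to control medically significant elevations in LDL-cholesterol which have been confirmed upon repeat testing". The note to Table 5-2 on fibrates, statins, niacin and ezetimibe gives the same trigger for changing a drug already in use: "Unless adjustment is required to treat medically significant increases in LDL that have been confirmed upon repeat testing".

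**The endpoint.** Protocol 2.2 has the secondary objective "To determine the effect of LMB763 on fasting lipid profile". Section 3.7 explains the interest in LDL: "Pruritus and LDL elevations have been noted in clinical trials with a bile acid derived FXR agonist". The same sentence adds that such elevations have not been noted in studies of LMB763 (the description of those studies is blank in the public text). The paragraph ends: "Both pruritus and serum lipids will be closely monitored in this study".

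**The analysis.** Protocol 11.5.1 covers "Log-transformed ratio to baseline % liver fat and fasting lipid profiles (total cholesterol, HDL, LDL, triglycerides" and applies the repeated measures ANCOVA of section 11.4.2. SAP 6.2.3 does the same: "Log-transformed ratio to baseline % liver fat and fasting lipid profiles as well as change from baseline % liver fat". SAP section 2 puts the fasting lipid profile among the key secondary parameters compared at Week 12 in the first interpretable results.

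**Concomitant drugs.** Protocol 6.11 records drug, dose and dates on the CRF. SAP 7.2 lists these data by treatment and subject but plans no table of them.

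**The concern.** A lipid drug started or increased under this exception follows a high LDL value. If LMB763 raises LDL, such changes will be more frequent on LMB763 than on placebo, and they will lower the later LDL values of the patients with the highest readings. Those values enter the model as they stand. The difference at Week 12 would then combine the effect of LMB763 with the effect of the drugs given to counter it, and so be pulled towards zero. Total cholesterol is exposed in the same way. From the planned tables, a reader could not tell a flat LDL curve that means no effect from one that means a treated effect.

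What is at stake is the secondary lipid estimate, on a signal that the protocol itself raises from another FXR agonist.

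**Working it through.** **1. Is there a rule for values after a lipid-drug change?** The documents give no LDL effect size, SD, power or start rate, so there is no planned figure to reproduce. The places where a rule could stand are these:

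- Protocol 11.5.1 and SAP 6.2.3: the model is named, with no censoring, adjustment, estimand or sensitivity analysis for lipid-drug changes.
- Protocol 11.1 and SAP section 4: the PD set excludes patients for protocol deviations with an impact on PD data. Treatment allowed by section 5.2 is not a deviation, so these values stay in.
- SAP 6.1.3: one added analysis sets values after a change to missing. It is written for ALT, concerns adjustment of the study drug, and runs only if the number adjusted is not small (for example, more than 20%). It does not reach lipid drugs.

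**2. How much could be hidden?** All inputs are assumptions: untreated LDL is normal with SD 25 mg/dL and mean 110 on placebo and 125 on LMB763 (true difference 15). Every patient above a threshold c, in either arm, starts a drug that multiplies LDL by 0.65. The threshold is set so that 5%, 10% or 20% of LMB763 patients start.

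- Threshold: c = 125 + 25 × z(1 − p), with p the LMB763 start rate.
- Placebo start rate: q = 1 − Φ((c − 110)/25).
- Observed difference in mg/dL: 15 − 0.35 × (E₁ − E₀), where E is the mean of LDL × [LDL > c] in each arm.
- Observed difference in mean log LDL: 0.1347 + (p − q) × ln 0.65, where 0.1347 is the true log difference under these distributions and ln 0.65 = −0.431.

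| p | c | q | mg/dL difference | hidden | log difference | hidden |
|---|---|---|---|---|---|---|
| 5% | 166.1 | 1.2% | 15 − 0.35 × (8.83 − 2.17) = 12.7 | 16% | 0.1347 − 0.0162 = 0.1185 | 12% |
| 10% | 157.0 | 3.0% | 15 − 0.35 × (16.89 − 4.99) = 10.8 | 28% | 0.1347 − 0.0302 = 0.1045 | 22% |
| 20% | 146.0 | 7.5% | 15 − 0.35 × (32.00 − 11.75) = 7.9 | 47% | 0.1347 − 0.0540 = 0.0807 | 40% |

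The planned analysis is on the log scale, so the last column applies.

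**3. When would the effect vanish?** On the log scale the observed ratio is exp[ln(1 + true rise) + x × ln(1 − r)], with x the excess share of LMB763 patients on a new drug and r its LDL reduction. For a true rise of 15% and r = 30%, it shows as 13.0%, 11.0% and 7.1% at x = 5%, 10% and 20%. Full cancellation needs x = ln 1.15 / −ln 0.70 = 39%, or 63% at r = 20% and 27% at r = 40%.

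**4. Would setting later values to missing recover the effect?** This was simulated with a true rise of 15%, between-patient log-SD 0.20, within-patient log-SD 0.12, a 35% reduction, and starts triggered by the rise from baseline at Day 42 and read at Day 84. The all-values estimate was about 12.5% with starts of 6% vs 1%, and about 6% with starts of 26% vs 7%. With values after the start set to missing, and baseline and Day 42 LDL kept in the model, the estimate was 15.0% in both cases. Simply dropping the treated patients gave 14.0% and 12.2%, so the values before the start must stay in.

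**The case against.** **The safety signal is kept elsewhere.** A reader might infer that the safety objective is biased too. The documents do not support that. Protocol 9.1 makes an abnormal laboratory value an adverse event when it requires therapy, so an LDL rise that leads to a new or increased drug is counted. SAP 7.2 tabulates adverse events by preferred term and treatment, with grade and drug relationship shown separately. Laboratory summaries by visit, values before the start and the medication listings add to this, and the sponsor monitors safety unblinded. This stands, and it limits the point to the secondary lipid estimate.

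**A rise with LMB763 is not shown.** Section 3.7 attributes LDL elevation to a bile acid derived agonist and says it has not been noted with LMB763. This stands: the 15 mg/dL is an assumption.

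**Using all values is legitimate.** As an estimate of the effect regardless of added treatment, it is defensible, particularly in a non-confirmatory study. But neither document states that choice.

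**The remedy leans on missing at random.** Starts depend on high LDL, so this is a fair challenge. It does not defeat the remedy when the triggering LDL is a scheduled value kept in the model (working, step 4). The remedy is less exact when an unscheduled test outside the model prompts the start.

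**The ALT parallel is weak.** That rule is conditional and concerns the study drug, so it is no precedent for a lipid-drug rule.

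**Conclusion.** The gap is real. Changes in lipid treatment triggered by LDL are permitted, the later values are analysed unchanged, and the planned tables do not show how often this happens in each arm. If LMB763 raises LDL, the Week 12 difference in LDL and total cholesterol may be understated.

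Under the stated assumptions, about 12% to 40% of the log-scale difference is hidden at start rates of 5% to 20% on LMB763. Those rates, the size of the rise and the potency of the added drug are all assumed. A trigger that must be medically significant and confirmed on repeat testing may well keep the real rate low.

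A reader might infer that an LDL increase would be masked altogether. That does not follow: for a 15% rise it takes an excess of roughly 27% to 63% of LMB763 patients on a new drug, and visits before the start are unaffected. The change is still worth making, because it is cheap and removes an ambiguity about a secondary endpoint.

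**What to change.** In SAP 6.2.3:

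1. State that the all-values analysis estimates the effect on lipids regardless of changes in lipid-lowering treatment.
2. Beside it, add a repeated measures ANCOVA of LDL, total cholesterol, HDL and triglycerides that sets values after a new or increased lipid-lowering drug to missing. Keep all values before the start in the model, and note that missing at random holds only if the triggering LDL is among them.
3. Tabulate by arm the number of patients with a start or increase and the study day of the first one.

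The cost is one further set of model runs and one table, from concomitant-medication data already on the CRF. Patient management does not change.

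Separately, Protocol 6.10 says that rescue medication is not allowed, while section 5.2 permits drugs for confirmed LDL elevations. The sponsor should reconcile the two.
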